### Measures (see Table 1)

Our proposed primary outcome for the definitive trial is a reduction in depression symptoms by end of trial (eBPI> no eBPI) according to the Moods and Feelings Questionnaire (sMFQ (45)), which is recommend to assess treatment response in the NICE guidance for treating depression in young people (46). The sMFQ was sensitive to improvement in previous UK-based RCTs of interventions for depression in young people (2,47,48).. [name]'s studies (2,47) suggest a five-point reduction on the MFQ represents the minimally clinically important difference for the assessment of superiority. ADAPT found a MFQ standard deviation of 14.6, so this size of a reduction would equate to an effect size of 0.34. These studies were of young people who had passed through the waiting list and we can find no reference waitlist studies, so current study will add value by gathering essential data to

inform the estimation of the minimum clinically important difference in this novel research population.

Table 1 Basic low intensity schedule for data collection

Construct	Measures for Young People	Baseline	10 weeks	18 weeks	>18 weeks
Depression	Moods and Feelings Questionnaire (Primary Outcome)	Х	Х	х	
Impairment	Strengths and Difficulties Questionnaire Impact scale	Х	Х	X	
Waiting list choice	Wait; return to referrer; withdraw		Х		
Quality of Life	EQ-5D-5L	X	Х	Х	
Services and personal costs	Client Service Receipt Inventory – Child Version			X	
Experience research processes				Х	Х
Experience of eBPI / waitlist	Process evaluation interview				Х
Experience of harms of psychological therapy questionnaire	Experience of harms of psychological therapy questionnaire			х	

Our secondary outcomes include the proportion of cases choosing to leave the waitlist at three months (eBPI> no eBPI); young people will choose whether they want: a) remain on the waitlist to be seen face-to-face, b) return to the care of their primary services or c) withdraw from services entirely. We will also assess impairment using the Strengths and Difficulties Questionnaire Impact Supplement (49), Quality of Life with the EQ-5D young person's version (50), and access to services for economic evaluation, which include support from education, third sector and informal sources as well as CYPMHS and other health services with the Client Services Receipt Inventory (CSRI; (51). We will assess acceptability measured by engagement in eBPI (time spent on the system, sessions logged into etc), retention and additional support required from CYPMHS and other services, as well as adverse effects using strategies developed in WP3.The schedule for measurement is illustrated in Table 1 and Figure 3. The low intensity data collection arm will collect baseline measures prior to randomisation, and at 10 weeks (which will be post-intervention for the eBPI arm) as well as at 18

weeks (months 28 to 31). The higher intensity data collection will add fortnightly completion of sMFQ from baseline until 10 weeks.

The **process evaluation** would determine if eBPI and our trial methods are feasible and acceptable for young people, parents, and clinicians. After the final follow up, young people and their parents from each study arm (n=10 eBPI vs. n=10 no eBPI; months 31 to 33) will be interviewed about their experiences of the intervention and other support received, as well as participation. The **health economic evaluation** will consist of a detailed calculation of the costs of the eBPI intervention, and analysis of resource use data collected during the study using the CSRI. As part of the process evaluation interviews, we will ask questions about service use and out of pocket costs to inform the data to be collected in a future **health economic evaluation**, as well as asking if "spill over effects" are incurred by parents or other family members. We will also ask about the best way to collect these health economic data, including mode and frequency of data collection.

A purposive sampling strategy would ensure a diversity of backgrounds and views are represented. Interviews will also be conducted with clinicians (n=10) at the end of the intervention delivery period to explore perceptions of the interventions' value, including anticipated benefits and harms. Interviews will be conducted face-to-face or via an online platform according to participant choice. Qualitative process interviews will commence with parents and young people as they complete the four month follow up and incorporate clinic staff once the services all patients from their CYPMHS have completed follow up.

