We have consent to participate from two NHS CYPMHS trusts that include 10 separate CYPMHS. These clinics serve diverse communities with significant variations in ethnicity, employment and educational characteristics, and their waitlist practice varies, providing a rich context for our study. Five services are part of the Berkshire NHS Foundation Trust (Newbury, Wokingham, Reading, Slough, and Bracknell), while the other five services are from Central and Northwest London NHS Foundation Trust (CNWL; Westminster, Kensington and Chelsea, Harrow, Hillingdon and Brent). Both the Trusts have a defined clinical pathway for young people with anxiety/depression who have been referred for specialist assessment / treatment. For Berkshire, anxious/depressed young people are placed on the waitlist for the severe emotional team (SET); CNWL place their anxiety/depressed adolescent cases on the mood disorder waitlist. In both trusts these waitlists include neurodiverse young people who additionally have depressed mood. Project leads in each NHS Trust ([name] in Berkshire and [name] in CNWL) will be responsible for supporting recruitment and the eBPI user's needs. They are also constituent members of the development and research team. From our collective experience, successful recruitment of patients attending CYPMHS depends on active involvement of the senior research staff with lead research clinicians in generating interest and involvement across the two NHS trusts, supplemented by energetic follow up by the research team. A clinical monitoring committee will monitor recruitment, engagement and retention from each clinic to share best practice and successful strategies.

We have scoped these waitlists; there are approximately 40 young people waiting for a face-to-face assessment and treatment per service (400 in total) with an estimated wait time of 36 to 52 weeks. We want to ensure the intervention cohort is representative of ethnic and cultural diversity in the catchment area, although we will be constrained by the population who seek help and are accepted

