Norwich CTU will randomly allocate young people to eBPI (n=40) or waiting as usual (n=40) at the individual level. Clinician support as provided by local CYPMHS policy will be available to both groups throughout. Because of the sex difference in the prevalence of depression in young people and our relatively small sample, we propose to stratify randomisation by sex assigned at birth so that we ensure some boys are recruited to each arm. We will stress to participants and participating clinics that **eBPI will be provided as part of, rather than instead of, being on the waiting list** because fear of losing their place is a common reason reported for not engaging in such interventions (44). Within each treatment group, we will additionally randomise to low intensity (baseline, post intervention and follow up; n=40) and higher intensity data collection (basic schedule plus fortnightly short version of the Moods and Feelings Questionnaire (MFQ; 45) until week 10; n=40; see Figure 3). The follow up schedule will remain unchanged for those who choose to come off the waiting list or are offered and accept treatment, unless they withdraw themselves from the study.

Figure 3 Data Collection Schedules

Low intensity data collection n=40

High intensity data collection n=40

We propose to recruit between 8 and 10 young people per clinic to generate a total of 80 and anticipate that recruitment will be completed within three months (months 21 to 24; 3 to 4 young people per clinic per month). The eBPI intervention will last for eight weeks (starting month 22 and completing by the end of month 27 depending on recruitment date and allowing two weeks after baseline to randomise and set up eBPI for the intervention arm. Data from our own trials and examination of current wait lists in two collaborating CYPMHS suggests that 95% of those waiting accept treatment when initially offered. Given 30% only attend one session (4) while 1 in 5 CYPMHS patients who entered the IMPACT trial only had a therapy 'dose' of 2 sessions, we estimate that between 15 to 30% will respond to eBPI and choose to leave the waiting list compared to those waiting as normal. This sample size is sufficient to provide data to test these assumptions.

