- 5. **Risk to self or others or child safe-guarding concerns:** These are likely to emerge during the delivery of eBPI but could emerge in any WPs during interviews or questionnaire completion. Research staff will all be trained to follow clear standing operating procedures agreed with the Project Management Group and Steering committee. These will be written guidelines that describe the procedures that should be taken when disclosures are made. If appropriate, relevant information will be fed into the CYPMHS processes and reported as a potential Serious Adverse Effect. They will be noted centrally to allow any patterns to be identified.
- 6. **Data security or ethics breach:** Our protocol and data management will be supported by explicit standard operating procedures and mandatory staff training on data governance and ethical research. There will be rapid reporting and review of any breaches involving the Project Steering Committee and NIHR as appropriate.
- 7. **Withdrawal of a clinical site from WP3:** We consider this unlikely as there are strong links between the co-applicants across sites leading to successful delivery of complex projects. Finally, [name], [name] and [name] have extensive collaborative child mental health networks and we are confident that if required, we could encourage an additional site (s) to join the study.

**Progression** to definitive trial would require the following success criteria to be met:

- Recruitment (target 40 per trust, 8 per clinic, total 80) progression recommended if a minimum of 60 were recruited.
- Engagement with eBPI in the treatment arm (target 40); minimal clinically relevant engagement will be assumed to be 2 activitations of eBPI but this will be refined during WPs 1 to 3 and reviewed after WP4. Progression would be recommended if 65% of those randomised engaged (this would be between 19 and 26 depending on recruitment figures).
- Retention (target 70 or 87%) progression recommended if **75% or more (ie 60 if 80 recruited)** were retained at 18 weeks:

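### The harms questionnaire is scheduled only at 18 weeks, about eight weeks after eBPI ends, although a 10-week assessment already exists that could carry it

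*Protocol*

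**What the plan says.** In the protocol's Measures section, the table titled "Table 1 Basic low intensity schedule for data collection" has a row for the "Experience of harms of psychological therapy questionnaire" with a single mark, under 18 weeks. The cells for baseline, 10 weeks and beyond 18 weeks are empty. The same table places the MFQ, the SDQ impact scale and the EQ-5D at baseline, 10 and 18 weeks, and the waiting-list choice at 10 weeks.

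The other data-collection schedule brings no further harms form: "The higher intensity data collection will add fortnightly completion of sMFQ from baseline until 10 weeks".

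On timing, the WP4 section says "The eBPI intervention will last for eight weeks", "allowing two weeks after baseline to randomise and set up eBPI for the intervention arm". The Measures text calls the 10-week assessment post-intervention for the eBPI arm. Young people who leave the list, or who take up an offer of treatment, stay on the same follow-up timetable unless they withdraw from the study. The queue is described as one "with an estimated wait time of 36 to 52 weeks".

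On other harm capture, the Measures section says the trial will assess acceptability "as well as adverse effects using strategies developed in WP3". No harms questionnaire at withdrawal is described.

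**The concern.** This is the only named questionnaire that asks about harms of therapy. Giving it once, at the last follow-up, has two consequences.

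- **Coverage.** Only participants still in the study at week 18 can answer. Someone who completes week 10 and is then lost has attended an end-of-intervention assessment without being asked.
- **Attribution.** The form asks about psychological therapy in general. A participant who has begun face-to-face treatment by week 18 may be answering about eBPI, about that treatment, or about both.

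Establishing safety is part of the programme's second objective, and the pilot is meant to show whether eBPI warrants a definitive trial. A harms measure taken close to the end of eBPI would serve both purposes better.

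**Working it through.** **1. Gap between the end of eBPI and the form** (WP4 and Measures sections). Set-up 2 weeks + eBPI 8 weeks = week 10. The form is at week 18, so the gap is 18 − 10 = 8 weeks. This is approximate, because two weeks is an allowance for set-up.

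**2. The protocol's own retention figures** (Success Criteria and Barriers). Target: 70/80 = 87.5%, given as 87%. Progression threshold: 0.75 × 80 = 60, as stated. Both reproduce.

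**3. Participants with no harms form.**

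| Retention at week 18 | Lost, both arms | Lost, eBPI arm if loss is equal |
|---|---|---|
| 70 of 80 (target) | 80 − 70 = 10 | 10/2 = 5 of 40 |
| 60 of 80 (threshold) | 80 − 60 = 20 | 20/2 = 10 of 40 |

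The protocol does not split loss by visit. A week-10 form would reach those lost between weeks 10 and 18. That is anywhere from 0 to 10 people at the target and 0 to 20 at the threshold. Those lost before week 10 could be reached only by a form at withdrawal.

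**4. Overlap with face-to-face treatment.** The documents do not give this share, so it needs an assumption about where recruits stand in the queue. Eligibility runs from joining the list until leaving it or being offered treatment, so entry could be early or late.

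- Entry at the start of a 36 to 52 week wait: nobody reaches the front by week 18, so overlap is near 0%, apart from those who deteriorate and need active treatment.
- Entry spread evenly along a wait of W weeks: the share reaching the front by week t is t/W.

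| | W = 52 | W = 36 |
|---|---|---|
| By week 10 | 10/52 = 19% | 10/36 = 28% |
| By week 18 | 18/52 = 35% | 18/36 = 50% |
| Between weeks 10 and 18 | 8/52 = 15% | 8/36 = 22% |

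Of 40 in the eBPI arm, even spread gives 14 to 20 by week 18, of whom 6 to 9 arise after week 10. Across these scenarios the overlap at week 18 runs from near 0% to about 50%. A week-10 form would reduce it but not remove it.

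**5. What loss could do to the harm rate (illustration only).** If loss is unrelated to harm, the rate among responders is not biased and only precision suffers. If, purely as an assumption, 10% of retained and 30% of lost eBPI participants had experienced harm, the true rate with 5 lost would be (35 × 0.10 + 5 × 0.30)/40 = 12.5%. With 10 lost it would be (30 × 0.10 + 10 × 0.30)/40 = 15%. The questionnaire would show 10% in both cases. The protocol has no data on whether loss is related to harm.

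**The case against.** The strongest reply is that one form at the end of follow-up covers the whole period and sits among several other routes. eBPI is to have codesigned ways of flagging distress or risk. WP3 is to collect quantitative data on adverse effects and develop strategies for WP4. Support given during the intervention is recorded and discussed. There is a risk and SAE procedure, and a clinical monitoring committee that expects to meet weekly. The MFQ and SDQ impact scale at week 10, and the fortnightly sMFQ in half the sample, would show worsening symptoms on a standard scale. All of this stands, and it limits the point to the questionnaire. It does not close the gap: symptom scales are not harms questionnaires, the WP3 strategies are not yet defined, and the process interviews cover 10 per arm after final follow-up.

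A reader might infer three stronger things that the documents do not support.

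- *That harms will be under-counted in the people most affected.* Selective loss of harmed participants is plausible but is an inference. Stopping eBPI is also not the same as leaving the study: anyone who stops, or misses week 10, but returns at week 18 is asked.
- *That week-18 answers can no longer be tied to eBPI.* This applies only to those treated before week 18. Even the higher scenarios above leave 50 to 65% not yet reached by an offer, and the service-use inventory at 18 weeks may help identify who had other treatment.
- *That week 10 should be the main harms result.* Harms may emerge after eBPI ends, and which time point leads is a debatable analysis choice. Nothing here settles it.

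A fair practical objection is that a form about psychological therapy means little to a waiting-as-usual participant who has had none. The copy of the table in the Study Summary is not legible enough in the text available to settle whether the form is meant for one arm or both. The fix has to allow for this.

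**Conclusion.** The point holds for the timing of this one questionnaire. It is given about eight weeks after eBPI ends and is absent from an assessment that already falls at the end of eBPI. At the protocol's own retention figures, 10 to 20 of 80 would not complete it, or about 5 to 10 in the eBPI arm assuming equal loss. How many of these a week-10 form would recover cannot be computed. The share whose week-18 answers may mix eBPI with face-to-face treatment is near 0% to about 50%, depending wholly on where in the queue recruits enter.

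The protocol contains no contradiction or wrong figure here, and harms are not otherwise unmonitored. This is an inexpensive improvement to the safety data, worth making before WP4 begins.

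**What to change.** In Table 1:

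- Add the harms questionnaire at the existing 10-week assessment, for the same participants who receive it at 18 weeks, with wording suited to waiting-as-usual participants who have had no therapy.
- Keep the 18-week form, so that later harms are still captured.
- Offer the form at withdrawal to anyone who leaves the study early.
- Report both time points by arm.

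The cost is one more form at an existing contact, an offer of the form at withdrawal and a small amendment to the table, with slightly more questionnaire burden at week 10. No additional visit is needed. As a side benefit, the interim review expects about half the sample to have reached week 10 and a quarter week 18. With 80 recruited, up to about 40 harms forms could exist by then instead of about 20. That review is aimed at recruitment, engagement and retention, but the earlier forms would also be available to the clinical monitoring committee.

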### Study participant support

The research team will support participants in all WPs with matters related to the research. Technical support for eBPI will be codeveloped in WP2, refined in WP3 and evaluated as part of WP4. We currently envisage a range of different modes that young people could use to access this support in real time, for example by chat function, direct message, or video / audio call. The policies and practices of each NHS Trust regarding the safety and well-being of waitlist cases will be adhered to during WP3 and 4, and WP1 and 3 will develop and refine standard operating procedures to facilitate this. The nature of any support given during intervention period will be recorded and discussed by the clinical monitoring committee during WP3 and 4.

### DISSEMINATION

We will work with PPIE members to develop a dissemination and impact plan. Young people and parents / carers will be actively involved in dissemination and engagement activities e.g. producing videos about the project using TikTok and creating a newsletter. This will include informing stakeholders of progress and results via social media, a study newsletter, and blogs such as Mental Elf. In line with INVOLVE recommendations, we will close the feedback loop on decision-making to ensure PPIE members know how their insights are being used.

### Outputs and anticipated impact will include:

- A novel eBPI platform that could support treatment for young people on waitlists.
- Standardised operating procedures for the safe delivery of eBPI within specialist CYPMHS that could provide a template for other studies.
- Knowledge about waitlist trajectories and reasons for leaving or staying on the waitlist and
  the impact of being on a waitlist on young people and their families that could inform
  service provision, commissioning, and policy; we will support this by producing policy
  briefings for commissioners and service providers, supplemented by blogs and podcasts for
  young people and families.
- Protocol of a definitive RCT to support application for subsequent study.
- Enhanced knowledge of recruitment and retention to improve the efficiency of mental health intervention trials in clinical populations of young people.
- Each WP will lead to at least one conference presentation, such as the British Association of Behaviour Cognitive Therapists and the European Society for Child and Adolescent Psychiatry.
- At least two academic papers for peer reviewed publication; the first from WPs 1,2 and 3 on
  the coproduction of eBPI will be submitted to *Journal of Medical Internet Research;*Formative Research and the second from WP4 will be submitted to Lancet Psychiatry. A
  further paper about strategies to maximise recruitment and retention and the impact (if
  any) of data collection intensity will be written if data permit.

### **PROJECT TIMETABLE**

The project will run from March 2024 until end of February 2027, but we will start preparing protocols for WPs 1 and 2 as soon as funding is secured as well as working towards the relevant ethical and trust approvals to minimise the chance of delay. Preparatory work with Acteon Communications LLP, the proposed technical partner, is already underway. Year 1 mainly comprise WP1, with WP2 starting in month 9. WP1 will explore the experience and expectations of waitlists from the perspective of young people, parents and clinicians. This will provide a map of current pathways and define the processes and criteria for the evaluation of patient experience and develop standardised operating procedures for WP3 and 4. WP2 comprising the coproduction of eBPI informed by the early findings from WP1. The timing of WP2 will overlap with both WP1 and WP3 (early testing of eBPI) to allow iterative feedback between codesign and early experience with the platform in CYPMHS. Norwich Clinical Trials Unit (NCTU) will carry out preparatory work from the beginning of year 2 to ensure a smooth operational implementation of the feasibility trial (WP4) in terms of trial and data management. During set-up, the CTU Research Lead will work with the

research team and Young People's Advisory Group to identify ways to maximise recruitment and retention, including acting on knowledge gained during earlier work packages, and reviewing previously published work (e.g. from the ORRCA recruitment and retention methodology database https://www.orrca.org.uk/). The initial approach, consent process, follow-up and other contact during the study will be carefully considered, and we anticipate building flexibility and choice into the study protocol to recruit young people to facilitate equality, diversity and inclusion. Identifying research processes that are feasible with this study population will be valuable for a subsequent definitive RCT but will also inform other researchers working with young people with depression. The pilot RCT will commence in month 21; quantitative data collection will complete in month 29 and the process evaluation in month 31, allowing five months for analysis, writing up and dissemination.

